## Revision Chronology

GlaxoSmithKline Document Number	Date	Version
2015N264314_00	2016-APR-06	Original
2015N264314_01	2016-JUN-15	Amendment No. 1

Section 4.6.1 and Section 7.1.1 have been adjusted slightly to make it clearer that subjects will be provided with a thermometer to be able to record temperature as part of capturing adverse event (AE) information.
 
In Section 5.2, exclusion criterion 13 has been updated to reflect the revised recommended alcohol consumption guidelines.
		
2015N264314_02	2016-AUG-17	Amendment No. 2

The protocol title and text have been amended to clarify that while the investigator and subjects are blinded the sponsor-is unblinded.
 
Details of the procedures required at early withdrawal visits have been added to the Time and Events Table, Section 7.1.
 
Details around the Safety Review Team have been added to include a consultant external to GSK to Section 6.3.
 
The inclusion and exclusion criteria have been updated in Section 5.1 and Section 5.2. and clarification around prohibited medications has been provided in Section 6.11.2. to align with updated exclusion criteria (Section 5.2).
 
Administrative changes have been made to the T&E table (Section 7.1) and text to ensure consistency throughout.
		
2015N264314_03	2017-MAY-26	Amendment No. 3

Changes in the Primary Medical Monitor and contact details.
 
Alignment of contraception requirements in Section 5.1 and Section 12.5.1 for partners of male subjects that are female of reproductive potential.
 
Section 5.1, Inclusion Criteria, has been updated to align with Section 12.5.1 contraception requirements for partners of male subjects that are female of reproductive potential. Changes made to these sections.
 
Section 5.1 Inclusion Criteria, bullets have been replaced with numbers.
		

2015N264314_04	2017-JUL-10	Amendment No. 4

Section 4.4 Design Justification, has been updated to permit earlier interim analysis.
 
Section 5.3, Screening Failures/Re-Screening, has been updated to allow re-screening.
 
Section 7.1.1 Time and Events Table – Screening Visit(s), has been updated to clarify timing of screening visits.
 
Section 10.2 Regulatory and Ethical Considerations, Including the Informed Consent Process, to clarify that a new ICF should be completed for each re-screened subject.
		

## 1. PROTOCOL SYNOPSIS FOR STUDY 205540

### Rationale

GSK2245035 is a highly selective Toll-like receptor 7 (TLR7) agonist that preferentially stimulates the induction of type I interferons. Intranasal (i.n.) administration of GSK2245035 in humans has been shown to cause immune changes in the upper airways milieu that may alter bystander immune responsiveness to aeroallergens and contribute to reduction of allergic reactivity in subjects with respiratory allergies.

In a 8-week repeat dose safety study (TL7116958) with i.n. GSK2245035 20 ng and 80 ng, target engagement was confirmed by dose-related increases in serum and nasal lavage interferon inducible protein-10 (IP-10) levels in subjects with symptomatic allergic rhinitis and mild asthma. Prolonged activation (up to 1 week in the serum and 3 weeks in nasal lavage) of the interferon (IFN)  $\alpha$  pathway was noted at the higher dose with no associated adverse effects during this follow-up period. Eight weekly doses of both 20 ng and 80 ng reduced nasal symptoms and allergic biomarkers after nasal allergen challenge and those reductions were sustained up to 3 weeks post treatment.

This study will assess whether TLR7-mediated pharmacology, with i.n. GSK2245035 20 ng administered weekly for a period of 8 weeks, will lead to reduced allergic reactivity in the lower airways in subjects with mild allergic asthma.

[figure not shown]
### Objective(s)/Endpoint(s)

Objectives	Endpoints
Primary	

 
To evaluate the effect of treatment with i.n. GSK2245035 compared to placebo on the allergen-induced late asthmatic response (LAR) in subjects with allergic asthma.
 
	
 
LAR: minimum forced expiratory volume in 1 second (FEV1) between 4-10 hours following allergen challenge one week after treatment.
 
LAR: weighted mean FEV1 between 4-10 hours following allergen challenge one week after treatment.
 

Secondary	

 
To evaluate the effect of treatment with i.n. GSK2245035 compared to placebo on the allergen-induced early asthmatic response (EAR) in subjects with allergic asthma.
 
	
 
EAR: minimum FEV1 between 0-2 hours following allergen challenge one week after treatment.
 
EAR: weighted mean FEV1 between 0-2 hours following allergen challenge one week after treatment.
 

Objectives	Endpoints

 
Safety
 
	

 
To evaluate the safety and tolerability of treatment with eight weekly doses of 20 ng i.n. GSK2245035
 
	
 
General safety endpoints including adverse events (AEs), peak expiratory flow (PEF), rescue salbutamol use, and clinical laboratory parameters
 

 
Exploratory
 
	

 
To evaluate the duration of effect of treatment with i.n. GSK2245035 compared to placebo on the allergen-induced asthmatic responses (LAR and EAR) in subjects with allergic asthma.
 
	
 
LAR: minimum and weighted mean FEV1 between 4-10 hours following allergen challenge approximately 4 and 12 weeks after treatment.
 
EAR: minimum and weighted mean FEV1 between 0-2 hours following allergen challenge approximately 4 and 12 weeks after treatment.
 


 
To evaluate the induction of TLR7-associated pharmacodynamic (PD) biomarkers and exhaled nitric oxide (FeNO) following treatment with i.n. GSK2245035
 
	
 
TLR7-induced blood PD biomarkers.
 
TLR7 induced gene expression changes in blood
 
TLR7-induced nasal fluid PD biomarkers
 
Change in FeNO levels during the treatment phase
 

 
To evaluate the effect of treatment with i.n. GSK2245035 compared to placebo on Bronchial Allergen Challenge (BAC) associated allergic biomarkers
 
	
 
Allergic biomarkers in induced sputum
 
Allergic biomarkers in blood
 
Change in FeNO levels following BAC
 

 
To evaluate the effect of treatment with i.n. GSK2245035 compared to placebo on Nasal Allergen Challenge (NAC) associated allergic biomarkers
 
	
 
Allergic biomarkers in nasal fluids
 
Cellular profile of nasal mucosa
 

 
To evaluate the effect of treatment with i.n. GSK2245035 compared to placebo on Intradermal allergen challenge
 
	
 
Mean diameter early phase response
 
Mean diameter late phase response
 

 
To evaluate the effect of treatment with i.n. GSK2245035 compared to placebo on total nasal symptoms
 
	
 
Total nasal symptoms score (TNSS) assessed daily (AM and PM) throughout the study treatment phase
 

 
To evaluate systemic pharmacokinetics (PK) after administration of i.n. GSK2245035
 
	
 
Plasma GSK2245035 concentrations
 

## Overall Design

This will be a randomised, double-blind (sponsor open), placebo-controlled, parallel group, 8-week treatment study. Study schematic below:

BAC -Bronchial allergen challenge; NAC – Nasal allergen challenge/administration  
 IC – Intradermal challenge; DV – Dosing Visit; FU – Follow-up

## Treatment Arms and Duration

- The study will consist of a screening period of up to approximately 4 weeks (involving two screening visits), a blinded treatment period of 8 weeks, followed by a follow-up period of up to 3 months. The total duration of the study for each subject will therefore be a maximum of approximately 6 months. All doses will be administered in the clinic.
- Approximately 24 subjects per arm will be randomised in a 1:1 ratio to receive either i.n. 20 ng GSK2245035 or placebo every week for the duration of 8 weeks.

## Type and Number of Subjects

- Subjects with allergic asthma who are sensitized to perennial or seasonal allergen(s) will be enrolled in the study. Based on the restriction of concomitant medications as shown in the exclusion criteria, the target population includes subjects with mild asthma not requiring maintenance treatment with inhaled corticosteroid who are able to be treated with short acting beta2-agonist (SABA) alone for the duration of the study (up until the final follow-up visit).

- A sufficient number of subjects will be enrolled to ensure that 20 per treatment arm complete the 8 week study treatment period and the BAC at the one week follow-up visit (one week after the 8th dose of study treatment).

## Analysis

Statistical models will be fitted separately to each primary endpoint. These endpoints will be analysed using analysis of covariance (ANCOVA) with treatment and baseline in the model; other covariates such as centre, allergen exposure ('presumed'/'unknown') and allergen exposure by treatment interaction may be included in the model.

Treatment comparisons of GSK2245035 vs Placebo will be presented with results also expressed as percentage attenuations to aid clinical interpretation. The posterior distribution for GSK2245035 vs Placebo will be obtained and expressed as percentage attenuation. The posterior probability of any percentage attenuation will be obtained, along with appropriate summary statistics from the posterior distribution (e.g. 70% equitail Credible Intervals).

The principle inferences are expected to come from models with non-informative priors. Sensitivity analyses using informative priors based on AstraZeneca (AZ) data may be fitted [Leaker, 2012].

An interim analysis will be conducted to assess how many subjects on placebo did not experience an LAR as such subjects will reduce the chances of establishing the primary objective of this study. This interim analysis will determine whether i) further recruitment into the trial should continue (i.e. a futility analysis), or ii) additional subjects should be enrolled to counteract the impact.

## 2. INTRODUCTION

### 2.1. Study Rationale/Brief background

The immunological milieu of the airways plays a critical role in shaping the nature of host responsiveness to inhaled allergens with predominant induction of aberrant Th2 responses driving the development of respiratory allergies and asthma. The scientific hypothesis is that intranasal delivery of a TLR7 agonist will activate local dendritic cells, inducing a type 1 IFN response, and result in the modification of the nature of both B and T cell responses to allergen. Driving the development of Th1/Treg responses may reduce the magnitude of mucosal Th2 reactivity and reduce local IgE responses.

GSK2245035 is a highly selective Toll-like receptor 7 (TLR7) agonist that stimulates preferentially the induction of type I interferons. In a 8-week repeat dose safety study (TL7116958) [GlaxoSmithKline Document Number [2013N174200\\_00](#)] with i.n. GSK2245035 20ng and 80 ng, target engagement was confirmed by dose-related increases in serum and nasal lavage IP-10, (interferon inducible protein 10) levels in subjects with symptomatic allergic rhinitis and mild asthma. Prolonged activation (up to 1 week in the serum and 3 weeks in nasal lavage) of the IFN $\alpha$  pathway was noted at the higher dose with no associated adverse effects during this follow-up period. Eight weekly doses of both 20 ng and 80 ng reduced nasal symptoms and allergic biomarkers

after nasal allergen challenge and those reductions were sustained up to 3 weeks post treatment.

Having demonstrated the effects i.n. GSK2245035 in patients with allergic rhinitis, this study will assess whether TLR7-mediated pharmacology, with i.n. GSK2245035 20 ng administered weekly for a period of 8 weeks, will lead to reduced allergic reactivity in the lower airways in subjects with mild allergic asthma using a bronchial allergen challenge model (BAC) at various time-points following treatment. For asthma patients who have allergic triggers for their disease, an i.n. treatment may be considered ideal to maximize co-localization with both its target, local dendritic cells, and aeroallergen. Clinical evidence to support the hypothesis that an intranasal TLR7 agonist can reduce the response to allergen in the lower airways using a BAC model has been reported ([Leaker](#) , 2012).

### 3. OBJECTIVE(S) AND ENDPOINT(S)

#### Objective(s)/Endpoint(s)

[figure not shown]
Objectives	Endpoints
Primary	

 
To evaluate the effect of treatment with i.n. GSK2245035 compared to placebo on the allergen-induced late asthmatic response (LAR) in subjects with allergic asthma.
 
	
 
LAR: minimum FEV1 between 4-10 hours following allergen challenge one week after treatment.
 
LAR: weighted mean FEV1 between 4-10 hours following allergen challenge one week after treatment.
 

Secondary	

 
To evaluate the effect of treatment with i.n. GSK2245035 compared to placebo on the allergen-induced early asthmatic response (EAR) in subjects with allergic asthma.
 
	
 
EAR: minimum FEV1 between 0-2 hours following allergen challenge one week after treatment.
 
EAR: weighted mean FEV1 between 0-2 hours following allergen challenge one week after treatment.
 

 
Safety
 
	

 
To evaluate the safety and tolerability of treatment with eight weekly doses of 20 ng i.n. GSK2245035
 
	
 
General safety endpoints including AE, peak expiratory flow (PEF), rescue salbutamol use, and clinical laboratory parameters
 

Objectives	Endpoints

 
• Exploratory
 
	

 
• To evaluate the duration of effect of treatment with i.n. GSK2245035 compared to placebo on the allergen-induced asthmatic responses (LAR and EAR) in subjects with allergic asthma.
 
	
 
• LAR: minimum and weighted mean FEV1 between 4-10 hours following allergen challenge approximately 4 and 12 weeks after treatment.
 
• EAR: minimum and weighted mean FEV1 between 0-2 hours following allergen challenge approximately 4 and 12 weeks after treatment.
 


 
• To evaluate the induction of TLR7-associated PD biomarkers and FeNO following treatment with i.n. GSK2245035
 
	
 
• TLR7-induced blood PD biomarkers.
 
• TLR7 induced gene expression changes in blood
 
• TLR7-induced nasal fluid PD biomarkers
 
• Change in FeNO levels during the treatment period
 

 
• To evaluate the effect of treatment with i.n. GSK2245035 compared to placebo on Bronchial Allergen Challenge (BAC) associated allergic biomarkers
 
	
 
• Allergic biomarkers in induced sputum
 
• Allergic biomarkers in blood
 
• Change in FeNO levels following BAC
 

 
• To evaluate the effect of treatment with i.n. GSK2245035 compared to placebo on Nasal Allergen Challenge (NAC) associated allergic biomarkers
 
	
 
• Allergic biomarkers in nasal fluids
 
• Cellular profile of nasal mucosa
 

 
• To evaluate the effect of treatment with i.n. GSK2245035 compared to placebo on Intradermal allergen challenge
 
	
 
• Mean diameter early phase response
 
• Mean diameter late phase response
 

 
• To evaluate the effect of treatment with i.n. GSK2245035 compared to placebo on total nasal symptoms
 
	
 
• Total nasal symptoms score (TNSS) assessed daily (AM and PM) throughout the study treatment phase
 

 
• To evaluate systemic pharmacokinetics (PK) after administration of i.n. GSK2245035
 
	
 
• Plasma GSK2245035 concentrations
 

## 4. STUDY DESIGN

### 4.1. Overall Design

- This will be a randomised, double-blind (sponsor open), placebo-controlled, parallel group, 8-week treatment study. Study schematic below:

BAC -Bronchial allergen challenge; NAC – Nasal allergen challenge/administration  
 IC – Intradermal challenge; DV – Dosing Visit; FU – Follow-up

### 4.2. Treatment Arms and Duration

- The study will consist of a screening period of up to approximately 4 weeks (involving two screening visits), a blinded treatment period of 8 weeks, followed by a follow-up period of up to 3 months. The total duration of the study for each subject will therefore be a maximum of approximately 6 months. All doses will be administered in the clinic.
- Approximately 24 subjects per treatment arm will be randomised in a 1:1 ratio to receive either i.n. 20ng GSK2245035 or placebo every week for the duration of 8 weeks.

### 4.3. Type and Number of Subjects

- Subjects with allergic asthma who are sensitized to perennial or seasonal allergen(s) will be enrolled in the study. Based on the restriction of concomitant medications as shown in the exclusion criteria, the target population includes subjects with mild asthma not requiring maintenance treatment with inhaled corticosteroid who are able

to be treated with short acting beta2-agonist (SABA) alone for the duration of the study (up until the final follow-up visit).

- A sufficient number of subjects will be enrolled to ensure that 20 per treatment arm complete the 8 week study treatment period and the BAC at the one week follow-up visit (one week after the 8th dose of study treatment).

If subjects prematurely discontinue the study, additional replacement subjects may be recruited and assigned the next available randomisation number, at the discretion of the Sponsor, in consultation with the investigator.

Following the interim analysis, additional subjects may also be enrolled to counteract the impact of individuals not exhibiting an LAR response on placebo.

Accounting for replacements and interim analysis recommendations, the total number of subjects to be randomised in this study is not expected to exceed 60.

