### 5.4. Withdrawal/Stopping Criteria

Reasons for withdrawal from the study may include:

- Use of a prohibited medication that cannot be safely discontinued while maintaining the subject's health.
- Treatment code is unblinded.
- Pregnancy: Any female subject who becomes pregnant.

The following actions must be taken in relation to a subject who fails to attend the clinic for a required study visit:

- The site must attempt to contact the subject and re-schedule the missed visit as soon as possible.
- The site must counsel the subject on the importance of maintaining the assigned visit schedule and ascertain whether or not the subject wishes to and/or should continue in the study.
- In cases where the subject is deemed 'lost to follow up', the investigator or designee must make every effort to regain contact with the subject (where possible, 3 telephone calls and if necessary a certified letter to the subject's last known mailing address or local equivalent methods). These contact attempts should be documented in the subject's medical record.
- Should the subject continue to be unreachable, only then will he/she be considered to have withdrawn from the study with a primary reason of "Lost to Follow-up".

A subject may withdraw from study treatment at any time at his/her own request, or may be withdrawn at any time at the discretion of the investigator for safety, behavioural or administrative reasons. If a subject withdraws from the study, he/she may request destruction of any samples taken, and the investigator must document this in the site study records.

Subjects withdrawn from the study while already exposed to IP will be asked to complete all safety assessments as outlined in the Time and Events Table (Section 7.1.2). Relevant pages of the case report form (CRF) should be completed by the investigator.

The replacement of withdrawn subjects will be at the discretion of the sponsor. If a subject misses one treatment dose, the investigator will consult with the GSK medical monitor as to whether the subject can receive further treatment. If more than one treatment dose is missed, then the subject may be withdrawn from the study, at the discretion of the Sponsor, in consultation with the investigator.

If subjects prematurely discontinue the study, additional replacement subjects may be recruited and assigned the next available randomisation number, at the discretion of the Sponsor, in consultation with the investigator.

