### **9.2. Sample Size Considerations**

The following was performed for each of the proposed LAR primary endpoints:

[figure not shown]
- Success criteria: declare endpoint success if the posterior probability of any treatment attenuation exceeds 0.7.
- The probability of declaring a success has been computed for a range of true percent attenuations and sample sizes (n per arm equal allocation). To make the figures easier to interpret the “nuisance” parameters of the placebo response and the standard deviation have been accounted for as follows:
- Eight previous GSK BAC studies (Crossover design) have been re-analysed to obtain estimates of the average placebo response and the associated estimate of residual variability applicable to the proposed Parallel Group design.
- These estimates were combined in a random effects meta-analysis to obtain posterior distributions for the underlying parameter values (placebo average response, residual variability (for an individual subject) and a between study variance component). The future placebo response was computed as the sum of random draws from the posterior distributions of the placebo average response parameter and a normal distribution with mean zero and variance equal to the between study variance parameter. The future GSK2245035 response was derived using the simulation scenario’s true percentage attenuation. A pooled sample variance value was generated using a Chi-Square distribution with degrees of freedom appropriate to the simulation scenario and a sampled variance from the meta-analysis posterior distribution. Those numbers were entered into the standard formulae for power curves. Repeating this process 10,000 times and taking the median of the resulting power values constructs “Assurance” operational characteristics for the combination of true percent attenuation and sample size under evaluation.

- These assurance operational curves have been summarised graphically. The x-axis is a hypothetical true drug effect that is assumed to be known for experimental design purposes.
- The simulations can also be used to compute the minimum observed percentage attenuations that would result in a successful study outcome. The median (of the 10,000 simulations) have been derived for a variety of sample sizes and success criteria (probability thresholds 0.7, 0.75, 0.8, 0.85, 0.95) and displayed graphically. The y-axis is the observed effect from the study data.

[figure not shown]

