Endpoint: LAR: minimum FEV1 between 4-10 hours following allergen challenge

- [Figure 1](#) illustrates the operating characteristics for the proposed design (n=20 completers per arm) that have a reasonable chance of meeting the definition of success.
- The best guess for the true treatment effect comes from the AZ study with AZD8848 in subjects with mild asthma, which dosed out of the allergen season and observed an approximately 18% effect size ([Figure 2](#)) [[Leaker](#) , 2012].

**Figure 1 LAR: minimum FEV1 between 4-10 hours following allergen challenge: Probability of Success (Assurance) with Success threshold of 0.7 (akin to a risk of false positives of 30%)**

[figure not shown]
**Figure 2** LAR: minimum FEV1 between 4-10 hours following allergen challenge: Minimum observed % attenuations needed to declare success for a variety of sample sizes and Success thresholds (levels of false positive risk)

[figure not shown]
- Endpoint: LAR: weighted mean FEV1 between 4-10 hours following allergen challenge

Figure 3 and Figure 4 are analogous to Figure 1 and Figure 2. The corresponding AZ point estimate was 27% attenuation. Similar conclusions can be drawn.

**Figure 3** LAR: weighted mean FEV1 between 4-10 hours following allergen challenge: Probability of Success (Assurance) with Success threshold of 0.7 (akin to a risk of false positives of 30%)

**Figure 4** LAR: weighted mean FEV1 between 4-10 hours following allergen challenge: Minimum observed % attenuations needed to declare success for a variety of sample sizes and Success thresholds (levels of false positive risk)

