**Table 2 Input data for Sample Size Work**

GSK Internal Study ID	LAR Minimum FEV1 between 4-10h			LAR Weighted Mean FEV1 between 4-10h		
	Average Placebo Response	Degrees of Freedom	Residual Variability	Average Placebo Response	Degrees of Freedom	Residual Variability
PPD	-1.3975	33.5	0.40571	-0.9462	33.1	0.30417
	-1.0864	45.9	0.13063	-0.7093	42.3	0.11430
	-1.1238	22.9	0.30521	-0.6916	22.8	0.18820
	-0.9006	48.9	0.07344	-0.3749	47.9	0.02191
	-0.7309	85.3	0.10717	-0.4662	84.4	0.07528
	-0.9027	31.9	0.27740	-0.5502	34.0	0.20925
	-1.4484	20.4	0.40528	-0.9817	20.3	0.31342
	-0.8129	69.6	0.15866	-0.5260	71.8	0.08695

Assuming the true treatment effect of GSK2245035 is no worse than the results from the AstraZeneca study and 20 subjects complete follow up assessments the probability of meeting the success criteria for Min LAR and WM LAR are approximately 78% and 81% respectively. This is considered sufficient justification for requiring 20 completers.

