7 PRIMARY STATISTICAL ANALYSES

7.1 Efficacy Analyses

7.1.1 Overview of Planned Efficacy Analyses

The primary efficacy analyses will be based on the PP population, unless otherwise specified. As a potential sensitivity analysis the final primary analysis model structure (derived using the PP population) may also be run using the mITT population (conditional on the PP and mITT populations differing).

Table 5 provides an overview of the planned efficacy analyses, with full details of data displays being presented in [Appendix 13: List of Data Displays](#).

Table 5 Overview of Planned Efficacy Analyses

Endpoint	Absolute							
	Stats Analysis			Summary		Individual		
	T	F	L	T	F	F	L	
LAR								
Min and WM FEV ₁ absolute change from saline at Week 9 (FUV1)	Y	Y	Y	Y	Y	Y	Y	

NOTES :

- T = Table, F = Figure, L = Listing, Y = Yes display generated.
- Stats Analysis = Represents TFL related to any formal statistical analyses (i.e. modelling) conducted.
- Summary = Represents TFL related to any summaries (i.e. descriptive statistics) of the observed raw data.
- Individual = Represents FL related to any displays of individual subject observed raw data.

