11 APPENDICES

Section	Appendix
RAP Section 4 : Analysis Populations	
Section 11.1	Appendix 1 : Protocol Deviation Management and Definitions for Per Protocol Population
RAP Section 5 : General Considerations for Data Analyses & Data Handling Conventions	
Section 11.2	Appendix 2 : Assessment Windows
Section 11.3	Appendix 3 : Treatment States & Phases
Section 11.4	Appendix 4 : Data Display Standards & Handling Conventions 
 • Study Treatment & Sub-group Display Descriptors • Baseline Definitions & Derivations • Reporting Process & Standards
Section 11.5	Appendix 5 : Derived and Transformed Data 
 • General, Study Population & Safety • Efficacy • Pharmacokinetic • Pharmacodynamic and or Biomarkers
Section 11.6	Appendix 6 : Premature Withdrawals & Handling of Missing Data 
 • Premature Withdrawals • Handling of Missing Data
Section 11.7	Appendix 7 : Values of Potential Clinical Importance 
 • Laboratory Values • ECG • Vital Signs
Section 11.8	Appendix 8 : Multicentre Studies
Section 11.9	Appendix 9 : Examination of Covariates and Subgroups
Section 11.10	Appendix 10 : Multiple Comparisons and Multiplicity
Section 11.11	Appendix 11 : Model Checking and Diagnostics for Statistical Analyses
Other RAP Appendices	
Section 11.12	Appendix 12 : Abbreviations & Trade Marks
Section 11.13	Appendix 13 : List of Data Displays
Section 11.14	Appendix 14 : Example Mock Shells for Data Displays (see separate document: RAP-Mock Tables-205540.doc)

11.1 Appendix 1: Protocol Deviation Management and Definitions for Per Protocol Population**11.1.1 Exclusions from Per Protocol Population**

The Protocol Deviation Management Plan (PDMP) contains more detail on the specific items that may cause subjects to be excluded from the per protocol population. In general a subject meeting any of the following criteria is expected to be excluded from the Per Protocol population (as described in the PDMP reviews and decisions will occur on a case by case basis):

Number	Exclusion Description
01	Failure of any inclusion/exclusion criteria, but subject is still enrolled.
02	Subject took short-acting beta-agonist (SABA) more than 2 days per week on average.
03	Subject did not receive all 8 doses of planned medication (Placebo or GSK2245035).

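### The 78%/81% probability of success assumes 20 analysable subjects per arm, but the recruitment target counts 20 completers, so the figures are not assured for the number analysed

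*Protocol*

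**What the plan says.** **The target.** Protocol 4.3 says enough subjects will be enrolled that "20 per treatment arm complete the 8 week study treatment period and the BAC at the one week follow-up visit". About 24 per arm are to be randomised (4.2), and the total randomised is not expected to exceed 60 (4.3). Replacement is discretionary and is offered for subjects who discontinue prematurely (4.3 and 5.4).

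**The justification.** Protocol 9.2 sets the rule: "declare endpoint success if the posterior probability of any treatment attenuation exceeds 0.7". If the true effect matches the external study of a similar agent and 20 subjects complete follow-up, 9.2.1 states that "the probability of meeting the success criteria for Min LAR and WM LAR are approximately 78% and 81% respectively". It offers this as the reason for requiring 20 completers.

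**The analysis.** Protocol 9.3.1 leaves any per-protocol set to the SAP. SAP 7.1.1 then says: "The primary efficacy analyses will be based on the PP population, unless otherwise specified". SAP 7.1.2 excludes observations with a missing covariate, such as baseline, from model fitting.

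**Ways a completer can drop out of that analysis.**
- SAP 11.1.1 lists expected per-protocol exclusions. They include an eligibility failure, SABA use on more than 2 days per week on average, and "Subject did not receive all 8 doses of planned medication". Protocol 5.4 leaves room for a missed dose: "If a subject misses one treatment dose, the investigator will consult with the GSK medical monitor as to whether the subject can receive further treatment".
- SAP 11.5.4 sets both LAR endpoints to missing if SABA was taken within 8 hours before the challenge, or if rescue was given between 0 and 4 hours.
- SAP 11.5.4 sets the baseline to missing when the allergen dose was modified for safety, although SAP 11.1.1 keeps that subject in the per-protocol set if the reduced dose is used consistently.

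**The concern.** The sample size rests on one argument: 20 per arm gives roughly an 80% chance of meeting the success rule. That argument belongs to 20 values per arm entering the primary model. The recruitment target guarantees something weaker, namely 20 people who finished treatment and underwent the FUV1 challenge. Neither document says how many of those are expected to be analysable or makes an allowance for the difference, and SAP 3.1 still projects the end of the study at 20 per arm.

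Some losses can occur without any breach of the protocol. Protocol 6.11.1 requires SABA to be withheld for at least 6 hours before a challenge visit, while SAP 11.5.4 voids the endpoint for use within 8 hours. A subject who follows the protocol can therefore lose both primary endpoints. The optional mITT run (SAP 7.1.1) does not recover a subject whose endpoint has been set to missing.

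**Working it through.** **Inputs**
- Success rule: posterior probability of any attenuation above 0.7 (Protocol 9.2). The figure captions call this "akin to a risk of false positives of 30" per cent. With non-informative priors it behaves like a one-sided test at 0.30, so the critical value is z = 0.524.
- Effect: the external study "observed an approximately 18% effect size" on minimum LAR, and 27% on weighted mean LAR (Protocol 9.2).
- Placebo response, unweighted mean of the eight studies in Protocol Table 2: −1.050 (Min), −0.656 (WM).
- Residual variance from the same table, mean / median: 0.233 / 0.218 (Min), 0.164 / 0.151 (WM).
- Loss rate among completers: not given, so a range of n is shown.

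**Formula**

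P(success) = Φ( δ / √(2σ²/n) − 0.524 ), where δ = attenuation × |mean placebo response| and n is the number analysed per arm.

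**Step 1: reproduce the stated figures at n = 20 (mean variance)**
- Min: δ = 0.18 × 1.0504 = 0.189; √(2 × 0.2329/20) = 0.1526; 0.189/0.1526 = 1.239; Φ(1.239 − 0.524) = 76.3%.
- WM: δ = 0.27 × 0.6558 = 0.177; √(2 × 0.1642/20) = 0.1281; 0.177/0.1281 = 1.382; Φ(1.382 − 0.524) = 80.4%.

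Median variance gives 77.5% and 82.0%. All four values are within 2 points of 78% and 81%, so the stated figures correspond to 20 analysed per arm. A noncentral t calculation changes these by no more than about 0.1 point. Reading the residual column as a standard deviation gives about 98% and 99.8%, and a two-sided 0.30 gives about 58% and 64%. Neither fits.

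**Step 2: reduce the number analysed** (range: mean to median variance)

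| n analysed per arm | Min LAR | WM LAR | Change from n = 20 (points) |
|---|---|---|---|
| 20 | 76.3–77.5% | 80.4–82.0% | – |
| 19 | 75.3–76.5% | 79.5–81.0% | −1.0 |
| 18 | 74.2–75.5% | 78.4–80.0% | −2.0 |
| 17 | 73.2–74.4% | 77.3–78.9% | −3.1 |
| 16 | 72.0–73.3% | 76.2–77.7% | −4.2 to −4.3 |
| 14 | 69.6–70.8% | 73.6–75.2% | −6.7 to −6.8 |

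Applied to the stated figures, 18 per arm gives about 76% / 79% and 16 per arm about 74% / 77%.

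**Step 3: check that the drop does not depend on the method.** An approximate version of the protocol's simulation (random-effects placebo response, chi-square sampled variance, median of the resulting power values) gives, at n = 20 / 18 / 16:
- common variance: Min 80.4 / 78.4 / 76.1%, WM 84.9 / 82.9 / 80.7%;
- between-study variance: Min 78.8 / 76.8 / 74.6%, WM 84.2 / 82.3 / 80.1%.

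The level shifts, and the WM median sits 3 to 4 points above the stated 81%; the exact meta-analysis priors are not in the documents. The drops remain about 2 and 4 points.

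**Step 4: compare with the cap of 60.** If 20% of completers were not analysable (an assumption), keeping 20 analysed needs 20/0.8 = 25 completers per arm. At the protocol's ratio of 24 randomised to 20 completing, that is 25 × 24/20 = 30 per arm, or 60 in total.

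**The case against.** A reader might infer that recruitment stops at 20 completers, so that any exclusion takes the analysed number below 20 and 78%/81% simply does not apply. The documents do not support that. Protocol 4.3 sets a minimum, and about 24 per arm are randomised. If 22 of 24 complete, two exclusions still leave 20.

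Other points in the plan's favour:
- Protocol 9.2.2 reports that success probabilities were computed for other sample sizes, including 15 and 20 per arm, and are held on file. The sponsor already has values that bracket 16 and 18. This stands, and it makes the restatement easy; it does not link the target to the analysis set.
- Per-protocol exclusions are expected rather than automatic, and are reviewed case by case (SAP 11.1.1). All doses are given in clinic, so completing treatment largely overlaps with receiving all eight. SAP 11.6.2.3 allows a missing baseline to be imputed, although SAP 7.1.2 says the record is excluded. These points reduce the likely loss but do not remove the endpoint rules. The automatic handling of missing responses in SAP 11.6.2.3 adds no information to a single-visit model.
- The effect is small against the plan's own yardstick. Protocol 4.4 triggers further review when non-reproducible LAR lowers the probability of success by more than 10%. By the Step 2 formula, a relative fall of that size needs about 13 analysed per arm: for Min with mean variance, Φ(0.999 − 0.524) = 68.2%, and 68.2/76.3 = 0.89. Nothing in the documents suggests losses that large. This stands and is why the severity is low.

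**Conclusion.** The point holds at low severity. The stated 78%/81% is a property of 20 contributing subjects per arm; the target guarantees 20 completers; and the primary model uses a subset of those. The figures are therefore not assured for the number analysed, which is a narrower statement than saying that they are wrong. Below 20 analysable, the cost is about 1 point per subject lost per arm. This rests on the Table 2 inputs, the external effect sizes taken as true, and the 0.7 threshold. How many subjects will be lost is unknown, and if 20 per arm remain analysable the stated figures stand. Separately, the 6-hour and 8-hour SABA passages contradict each other in effect and need reconciling whatever the loss rate.

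**What to change.** - **Protocol 9.2.1:** state that 78%/81% assumes 20 analysable subjects per arm, and give the corresponding values at 16 and 18.
- **Protocol 4.3 and SAP 3.1:** count the 20 as subjects with a valid FUV1 LAR endpoint, a Screening Visit 2 baseline, and no per-protocol exclusion known by FUV1, tallied blinded to treatment. The limit to what is known by FUV1 is needed because the allergen-dose criterion in SAP 11.1.1 depends on all follow-up challenges, the last at Week 20. SAP 4.1 already tracks deviations during the study and reviews them before unblinding.
- **Protocol 4.3 and 5.4:** add a clause extending discretionary replacement to completers who are not evaluable, within the existing expected maximum of 60. The present wording does not cover them.
- **Protocol 6.11.1 and SAP 11.5.4:** reconcile the SABA passages, so that following the protocol cannot by itself void the primary endpoint.

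The cost is a few sentences, a slightly less favourable stated figure if losses are expected, and possibly a few replacements. Replacements share the maximum of 60 with any interim increase towards 30 per arm, so the two should be considered together.
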